Amendment 2	14-OCT-2020	The study protocol has been revised to require (1) A minimum of 6 participants less than 17 years of age for each of the HGG, RMS, and EWS/pPNET target tumor cohorts, (2) Reduced PK sampling in children weighing <13 kg (3) Reduced PD sampling for children <16 kg (4) Medications known to prolong the QT interval are to be initiated cautiously; and (5) Added a requirement to normalize electrolytes prior to starting treatment per the lenvatinib SmPC and to also specify on study that electrolytes should be replenished as appropriate. Dose modification guidelines for QT interval prolongation to align with lenvatinib development program was also added.
Amendment 1/Czech Republic-specific amendment	18-AUG-2020	To address feedback from Czech Republic regulatory authorities.
Original Protocol	26-FEB-2020	Not applicable

PROTOCOL AMENDMENT SUMMARY OF CHANGES

Amendment: 04

Overall Rationale for the Amendments:

Further enrollment of participants into the other solid tumors' cohort was discontinued due to insufficient antitumor activity with lenvatinib for this patient population, with FDA and EMA agreement obtained.

Summary of Changes Table:

Section # and Name	Description of Change	Brief Rationale
1.1 Synopsis 4.4 Beginning and End of Study Definition 9.7.2 Efficacy Interim Analysis	Added text indicating that enrollment into the other solid tumors cohort was discontinued	Insufficient antitumor activity of lenvatinib in participants in the other solid tumors' cohort; FDA and EMA agreement obtained.
10.7.3 Italy	Included details regarding maximum blood volumes and a reference to "Ethical Considerations for Clinical Trials on Medicinal Products Conducted With Minors" [European Commission 2017]	To address the Italian Health Authority's recommendation to stipulate maximum blood volumes to be taken from participants in Italy
1.3 Schedule of Activities 8 Study Assessments and Procedures 8.3 Safety Assessments	Added references to Appendix 7 (Country-specific Requirements) where needed	

Section # and Name	Description of Change	Brief Rationale
1.3 Schedule of Activities 8.3.6.1 Hematology and Clinical Chemistry	Updated text to clarify that hematology, blood chemistry, and urinalysis samples are to be obtained and assessed, and the results are to be reviewed, prior to study drug administration on C1D1 and within 72 hours prior to the visit for all subsequent cycles	To clarify timing of study assessments
1.1 Synopsis	Added a statement acknowledging that the EWS and HGG cohorts were not expanded.	For completeness; fertility was concluded in the corresponding cohorts in Study E7080-A001-216.
5 Study Population	Added text regarding the collection and use of demographic data	To clarify the collection, use, and confidentiality of demographic data provided by the participants.
Title Page Section 10.1.1 Code of Conduct for Clinical Trials	Sponsor entity name and address change	Merck Sharp & Dohme Corp. underwent an entity name and address change to Merck Sharp and Dohme LLC, Rahway, NJ, USA. This conversion resulted only in an entity name change and update to the address.
8.4.7 Events of Clinical Interest	Added text to indicate that lenvatinib overdose is not considered an ECI	To clarify the reporting of lenvatinib overdose
10.3.2 Definition of AE	Formerly Section 10.3.1 Revised text to clarify that lenvatinib overdose without an associated AE is not reportable as an AE Added a reference to Section 8.5 (Treatment of Overdose)	

Section # and Name	Description of Change	Brief Rationale
8.4.5 Pregnancy and Exposure During Breastfeeding	
Added text to ensure that any pregnancy complications, as well as the medical reason for elective termination of a pregnancy, are reported as AEs or SAEs
 
Added ‘ectopic pregnancy’ to the list of pregnancy outcomes to be reported as serious events (Important Medical Events)
	To ensure that all pregnancy complications, outcomes, and medical reasons for elective termination of a pregnancy are properly reported
1.1 Synopsis 4.4 Beginning and End of Study Definition	Replaced withdraws ‘from the study’ with withdraws ‘consent’	To clarify the intent regarding the end of the study
8 Study Assessments and Procedures	
Added text “or dental”
 
“All study-related medical or dental decisions must be made by an investigator who is a qualified physician.”
	To correct a previous omission
1.1 Synopsis 6.1 Study Intervention(s) Administered	In the ‘Use’ column, replaced ‘Experimental’ with ‘Test Product’	To align with EU CTR
4.4 Beginning and End of Study Definition	
Added definition of end of study for analysis and reporting purposes
 
Added definition of local start of the study for countries in the EEA
	

Section # and Name	Description of Change	Brief Rationale

1 PROTOCOL SUMMARY

1.1 Synopsis

Protocol Title: An Open-Label, Multicenter Phase 2 Basket Study to Evaluate the Antitumor Activity and Safety of Lenvatinib in Children, Adolescents, and Young Adults with Relapsed or Refractory Solid Malignancies

Short Title: Lenvatinib for Pediatric Patients with Relapsed/Refractory Solid Tumors

Acronym: Protocol 013 (E7080-G000-231)

Hypotheses, Objectives, and Endpoints:

In children, adolescents, and young adults with relapsed or refractory solid malignancies treated with lenvatinib:

Primary Objectives	Primary Endpoints
- To determine the ORR at Week 16, by each tumor type, per RECIST 1.1 or RANO (for HGG only) as assessed by the investigator.	- Objective Response, defined as a confirmed (≥ 4 weeks after initial response) CR or PR.
Secondary Objectives	Secondary Endpoints
- To evaluate ORR, by each tumor type, per RECIST 1.1 or RANO (for HGG only) as assessed by the investigator.	- Objective Response, defined as a confirmed (≥ 4 weeks after initial response) CR or PR.
- To evaluate PFS per RECIST 1.1 or RANO (for HGG only), by each tumor type.	- PFS defined as the time from the date of the first administration of lenvatinib until the date of first documentation of PD or death (whichever occurs first).
- To evaluate the BOR, DOR, DCR, and CBR, by each tumor type.	- BOR defined as the participant's best confirmed response (CR or PR) over the treatment period. - DOR defined as the time from the date of the first documented CR or PR to the date first documentation of progressive disease or death (whichever occurs first). - Disease control defined as a BOR of CR or PR, or SD. To be assigned a BOR of SD, the time from the first administration of study drug until the date of documented SD should be ≥ 7 weeks. - Clinical benefit defined as a BOR of CR or PR, or durable SD (SD duration ≥ 23 weeks since the first dose of the study treatment).

- To evaluate the safety of lenvatinib.	- AEs, SAEs, clinical laboratory values, vital signs, 12-lead ECGs, urine dipstick, Lansky play scores or Karnofsky performance status scores, physical examination findings, dental examination findings, height, and closure of proximal tibial plates.
- To assess the palatability and acceptability of the suspension formulation of lenvatinib.	- Palatability questionnaire using a facial hedonic scale.
- To characterize the PK of lenvatinib.	- Assessment of population-based PK parameters of lenvatinib.

Overall Design:

Study Phase	Phase 2
Primary Purpose	Treatment
Indication	Treatment of relapsed/refractory pediatric solid tumors including: HGG, RMS, or EWS/pPNET and other solid tumors, excluding osteosarcoma.
Population	Children, adolescents, and young adults with relapsed/refractory HGG, RMS, or EWS/pPNET, or other solid tumors, excluding osteosarcoma. Participants with HGG, RMS and EWS/pPNET may only be enrolled in the tumor-specific cohorts and may not be enrolled in the other solid tumors' cohort. Participants with CNS tumors other than HGG are eligible for enrollment into the other solid tumors' cohort.
Study Type	Interventional
Intervention Model	Single Group This is a multi-site study.
Type of Control	None
Study Blinding	Unblinded Open-label
Blinding Roles	No Blinding
Estimated Duration of Study	The Sponsor estimates that the study will require approximately 42 months from the time the first participant (or their legally acceptable representative) provides documented informed consent/assent until the last participant's last study-related contact.

Number of Participants:

A minimum of 36 participants will be enrolled, 9 evaluable participants in each of 4 cohorts: HGG, RMS, EWS/pPNET, and other solid tumors. The final sample size of participants will depend on the number of tumor types that meet the futility bar and the antitumor activity in evaluable participants observed in the corresponding tumor cohort in Study E7080-A001-216. The enrollment in the HGG, RMS, and EWS/pPNET cohorts is capped at a maximum of 17 evaluable participants each. The enrollment for each tumor type expanded based on response in the other solid tumors' cohort is also capped at a maximum of 17 evaluable participants. Based on these factors and the projected enrollment period, it is estimated that up to approximately 150 participants could be enrolled. Participants will meet the criteria for being evaluable for an objective response if they have measurable disease present at baseline and at least 1 postbaseline efficacy assessment, unless they have discontinued prior to the first efficacy assessment due to progressive disease. Participants who are not evaluable for objective response will be replaced.

Intervention Groups and Duration:

Intervention Groups	
  
 Intervention Group Name	Drug	Dose Strength	Dose Frequency	Route of Admin.	Regimen/ Treatment Period	Use	
   
 	Lenvatinib	14 mg/m² (maximum daily dose of 24 mg)	Once Daily	Orally	Daily	Test Product	
  
	Intervention Group Name	Drug	Dose Strength	Dose Frequency	Route of Admin.	Regimen/ Treatment Period	Use		Lenvatinib	14 mg/m ² (maximum daily dose of 24 mg)	Once Daily	Orally	Daily	Test Product
	Intervention Group Name	Drug	Dose Strength	Dose Frequency	Route of Admin.	Regimen/ Treatment Period	Use								
	Lenvatinib	14 mg/m ² (maximum daily dose of 24 mg)	Once Daily	Orally	Daily	Test Product									
Total Number	1 arm														
Duration of Participation	
Each participant will participate in the study from the time the participant provides documented informed consent/assent through the final contact.
 
After a Screening phase of up to 28 days, each participant will be assigned to receive study intervention with lenvatinib. Participants will continue to receive lenvatinib until disease progression is verified by the investigator using RECIST 1.1 or RANO (for participants with HGG) criteria, initiation of another anticancer therapy, development of unacceptable toxicity, or withdrawal of consent, whichever occurs first. Estimated time of lenvatinib treatment is 1 year. However, participants can continue on treatment with lenvatinib until a treatment discontinuation criterion is met.
 
At the end of treatment, each participant will be followed for 30 days for the occurrence of AEs/SAEs and for spontaneously reported pregnancy as described in Section 8.4.
														

	
Participants who discontinue lenvatinib treatment for reasons other than radiographic disease progression or initiation of new anticancer therapy will have post-treatment follow-up imaging for disease status every 8 weeks for up to 24 weeks, then every 12 weeks thereafter until documentation of disease progression or start of a new anticancer agent, whichever occurs first, unless the participant withdraws consent, becomes lost to follow-up, or the study is terminated. Participants who discontinue lenvatinib treatment due to documented radiographic disease progression or initiation of new anticancer therapy will move to survival follow-up.
 
Participants will be followed by telephone every 12 weeks for survival status until death unless the participant withdraws consent, becomes lost to follow-up, or the study is terminated.
 
A database lock for the primary analysis will occur when all participants in all cohorts have discontinued the study or if the last evaluable participant has completed the Week 16 imaging assessment, whichever comes first.
 
Enrollment will be stopped for a specific cohort/tumor type if no objective responses occur in the first 9 evaluable participants (i.e., the futility boundary is crossed), or a lack of antitumor activity is concluded for the corresponding tumor cohort in Study E7080-A001-216.
 
EWS and HGG cohorts were not expanded because futility was concluded for the corresponding cohorts in Study E7080-A001-216. Further enrollment of participants into the other solid tumors' cohort was discontinued due to insufficient antitumor activity of lenvatinib in this patient population.
 
The overall study ends when the last evaluable participant completes the last study-related telephone call or visit, withdraws consent, or is lost to follow-up (ie, the participant is unable to be contacted by the investigator).
 
Additional details are in Section 4.1.

--	---

Study Governance Committees:

Steering Committee	No
Executive Oversight Committee	No
Data Monitoring Committee	Yes
Clinical Adjudication Committee	No
Study governance considerations are outlined in Appendix 1.	

[figure not shown]
Study Accepts Healthy Volunteers: No

A list of abbreviations used in this document can be found in Appendix 15.

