1.3 Schedule of Activities

Table 1 Schedule of Activities

Study Period	Screening	Intervention Cycle = 28 Days								EOT	Post-treatment Visits			NOTES
		1			2		3	4	5 – last		Safety FU	Efficacy (Imaging) FU Visits	Survival FU	
Cycle Day		1	8	15	1	15	1	1	1	At DC	30 days after last dose	Q8W for 24 weeks, then Q12W	Q12W	
Scheduling Window	-28 to -1		±2	±2	±2	±2	±2	±2	±2		±7	±7	±7	
Administrative Procedures														
Informed Consent/ Assent	X													Documented informed consent/assent may be obtained up to 4 weeks prior to C1D1 and must be obtained prior to performing any protocol-specified procedure. Results of a test performed as part of routine clinical management are acceptable in lieu of a screening test if performed within the specified time frame for screening.
Inclusion/ Exclusion Criteria	X													See Appendix 7 for country-specific requirements.
Participant Identification Card	X													At the time of allocation, site personnel will add the allocation number to the identification card.
Demographics	X													

Study Period	Screening	Intervention Cycle = 28 Days								EOT	Post-treatment Visits			NOTES
		1			2		3	4	5 – last		Safety FU	Efficacy (Imaging) FU Visits	Survival FU	
Visit Timing/ Cycle No.		1	8	15	1	15	1	1	1	At DC	30 days after last dose	Q8W for 24 weeks, then Q12W	Q12 W	
Cycle Day		1	8	15	1	15	1	1	1					
Scheduling Window	-28 to -1		±2	±2	±2	±2	±2	±2	±2		±7	±7	±7	
Medical/ surgical history	X													
Prior anticancer medication/ procedures	X													
Prior/ Concomitant medication review	X	X	X	X	X	X	X	X	X	X	X		X	Concomitant medications will be recorded throughout the study and for 30 days after last dose. Off-study anticancer therapy will be recorded from study treatment discontinuation until time of death or until withdrawal from survival FU.
Cancer staging as appropriate for pediatric tumor type	X													

Study Period	Screening	Intervention Cycle = 28 Days					EOT	Post-treatment Visits			NOTES			
		1		2		3		4	5 – last	Safety FU		Efficacy (Imaging) FU Visits	Survival FU	
Visit Timing/ Cycle No.		1	8	15	1	15	1	1	1	At DC	30 days after last dose	Q8W for 24 weeks, then Q12W	Q12 W	
Cycle Day		1	8	15	1	15	1	1	1	At DC	30 days after last dose	Q8W for 24 weeks, then Q12W	Q12 W	
Scheduling Window	-28 to -1		±2	±2	±2	±2	±2	±2	±2		±7	±7	±7	

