8.4 Adverse Events, Serious Adverse Events, and Other Reportable Safety Events

The definitions of an AE or SAE, as well as the method of recording, evaluating, and assessing causality of AE and SAE and the procedures for completing and transmitting AE, SAE, and other reportable safety event reports can be found in Appendix 3.

Adverse events, SAEs, and other reportable safety events will be reported by the participant (or, when appropriate, by a caregiver, surrogate, or the participant's legally authorized representative).

The investigator and any designees are responsible for detecting, documenting, and reporting events that meet the definition of an AE or SAE as well as other reportable safety events. Investigators need to document if an SAE was associated with a medication error, misuse, or abuse. Investigators remain responsible for following up AEs, SAEs, and other reportable safety events for outcome according to Section 8.4.3.

The investigator, who is a qualified physician, will assess events that meet the definition of an AE or SAE as well as other reportable safety events with respect to seriousness, intensity/toxicity and causality.

Progression of the cancer under study is not considered an AE as described in Section 8.4.6 and Appendix 3.

8.4.1 Time Period and Frequency for Collecting AE, SAE, and Other Reportable Safety Event Information

All AEs, SAEs, and other reportable safety events that occur after the participant provides documented informed consent but before intervention allocation must be reported by the investigator if the participant is receiving placebo run-in or other run-in treatment, if the event cause the participant to be excluded from the study, or is the result of a protocol-specified intervention, including but not limited to washout or discontinuation of usual therapy, diet, or a procedure.

- All AEs from the time of intervention allocation through 30 days following cessation of study intervention must be reported by the investigator.
- All AEs meeting serious criteria, from the time of intervention allocation through 30 days following cessation of study intervention.
- All pregnancies and exposure during breastfeeding, from the time of intervention allocation through 30 days following cessation of study intervention.

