8.11.5 Post-treatment Visits

8.11.5.1 Safety Follow-up Visit

The mandatory Safety Follow-up Visit should be conducted approximately 30 days after the last dose of study intervention or before the initiation of a new anticancer treatment, whichever comes first.

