9.6.2 Statistical Methods for Safety Analyses

Safety and tolerability will be assessed by clinical review of all relevant parameters, including AEs, laboratory tests, and vital signs. Safety summaries will be pooled across all indications. The additional safety analyses for each tumor type might be conducted if desired and will be documented in the sSAP. The safety analysis population will be used for the analysis of safety data. TEAE is defined as all AEs from the treatment start date until 30 days after last dose (30 days for SAE). The incidence of TEAEs and SAEs will be summarized by system organ class and preferred term. Continuous measures such as changes from baseline in laboratory test data, vital signs, 12-lead ECGs, cardiac function by echocardiography or MUGA scan, urine dipstick, and Lansky play scores or KPS scores will be summarized using descriptive statistics (mean, standard deviation, etc.) for baseline, on-treatment, and change-from-baseline values.

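### Section 9.6.2 defines TEAEs by date alone, so events that begin after a new anticancer therapy enter the lenvatinib safety tables with no cut and no flag

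*Combined protocol and SAP*

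**What the plan says.** **Collection.** Section 8.4.1 sets the reporting duty: "All AEs from the time of intervention allocation through 30 days following cessation of study intervention must be reported by the investigator". For serious events it is the same: "All AEs meeting serious criteria, from the time of intervention allocation through 30 days following cessation of study intervention". The synopsis repeats the 30 days in its description of participation: "each participant will be followed for 30 days for the occurrence of AEs/SAEs".

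**Analysis.** Section 9.6.2 reads "TEAE is defined as all AEs from the treatment start date until 30 days after last dose (30 days for SAE"; it then plans that "The incidence of TEAEs and SAEs will be summarized by system organ class and preferred term" and adds that "Safety summaries will be pooled across all indications". It names no table by causality and makes no provision for events after a further anticancer therapy.

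**Where new therapy is mentioned.** Section 8.11.5.1 places the Safety Follow-up Visit "approximately 30 days after the last dose of study intervention or before the initiation of a new anticancer treatment, whichever comes first". Section 8.3.6, on repeating clinically significant abnormal laboratory tests, has a branch for participants who begin new anticancer therapy, but that branch is also 30 days. The synopsis and Section 6.5.1 make starting another anticancer therapy a reason for lenvatinib to stop.

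**Data available.** The Schedule of Activities states: "Off-study anticancer therapy will be recorded from study treatment discontinuation until time of death or until withdrawal from survival FU".

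**The concern.** Evaluating the safety of lenvatinib is a secondary objective, and the study has one arm with no control. An all-cause TEAE table from such a study is usually read as a description of the drug. Participants have relapsed or refractory disease and stop mainly at progression. Some will move to another treatment, and for some that move is what ends lenvatinib. Any AE reported after that point and within 30 days of the last lenvatinib dose meets the definition in 9.6.2, whatever caused it.

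The protocol recognises the overlap when it schedules the safety visit but does not carry it into the analysis definition. Events that may belong to the next regimen are therefore mixed with lenvatinib events in the same rows, and the planned tables give the reader no means of telling them apart. The primary ORR analysis and the futility decisions are not affected.

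**Working it through.** There is no figure in the plan to reproduce. The check has two parts: a comparison of the passages, then an illustration of size.

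**1. Does any passage close the TEAE window at a new therapy?**

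| Section | Window | Effect of a new anticancer therapy |
|---|---|---|
| Synopsis | 30 days after end of treatment | none |
| 8.4.1, AEs and SAEs | allocation to 30 days after cessation | none |
| 9.6.2, TEAE | treatment start to 30 days after last dose | none |
| 8.3.6, repeat laboratory tests | 30 days, or 30 days if new therapy starts | min(30, 30) = 30, so none |
| 8.11.5.1, safety visit | about 30 days | visit moves earlier; the AE window does not |

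None does.

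**2. How much of the window can overlap?** If new therapy starts on day d after the last dose, the overlap is (30 − d)/30.

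- d = 7: 23/30 = 77%
- d = 14: 16/30 = 53%
- d = 21: 9/30 = 30%
- New therapy starts as lenvatinib stops (d near 0): close to the whole window

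Section 6.7 equates 1 week with 5 half-lives. On that figure about 2^−5 = 3% of the drug remains on day 7, with 23 days of the window still to run. This says nothing about how late a lenvatinib toxicity may first appear.

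**3. Illustration of size.** Inputs:

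- b, base Grade 3 or higher TEAE rate: 20/31 = 64.5%, from the Study 207 osteosarcoma cohort (Section 2.2.1.2). It is taken as free of events from later therapy.
- f, share of participants starting new therapy inside the 30 days: assumed.
- q, share of those with a Grade 3 or higher event caused by the new therapy inside the window: assumed.

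A participant already counted adds nothing to a participant-level incidence. With independence, the net rise is (1 − b) × f × q, and 1 − b = 11/31 = 0.355.

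| Assumptions | f × q | Net rise |
|---|---|---|
| Lower set, minimum: f = 10%, q = 10% | 0.01 | 0.355 × 0.01 = 0.4 points |
| Lower set, maximum: f = 50%, q = 50% | 0.25 | 0.355 × 0.25 = 8.9 points |
| Higher set, minimum: f = 20%, q = 30% | 0.06 | 0.355 × 0.06 = 2.1 points |
| Higher set, maximum: f = 50%, q = 60% | 0.30 | 0.355 × 0.30 = 10.7 points |

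Together the two sets span about 0.4 to 11 points. The dilution factor 1 − b is nearer 1 for a single preferred term that is rare on lenvatinib, so less of the effect is absorbed there. On the other hand, q for one term is smaller than q for any event.

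**The case against.** The strongest reply is that a TEAE here is deliberately an all-cause, time-based count. It already includes events due to the underlying disease, and choosing where the window ends is partly preference. A cut at new therapy has its own cost: those who switch fastest get the shortest observation, and delayed lenvatinib effects leave the cut table. This stands, and it is why the full 30-day table should remain beside the cut one.

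Second, the data for attribution exist. Investigators assess causality under Section 8.4, off-study therapy is recorded, and the supplemental SAP, which is not available here, might add tables. This also stands in part. But 9.6.2 plans no such separation, and it refers to the supplemental SAP only for optional safety analyses by tumor type.

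Third, overlap may be uncommon. Sections 2.1 and 4.2 describe patients without available or standard options. That does not exclude early switching; the intervals this protocol itself requires after prior therapy include 7, 14 and 21 days for some treatment classes. The frequency remains unknown.

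Several stronger readings are tempting and are not supported:

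- *That the 30-day collection window is wrong.* It is not. Reporting to Day 30 is what keeps delayed events visible. Only the analysis definition needs work.
- *That f × q, which reaches 6% to 30% under the higher assumptions, is the bias in the Grade 3 or higher rate.* It is the assumed share carrying an event from another treatment, not the net change in incidence, and neither factor comes from the documents.
- *That every event after a switch belongs to the next regimen.* These participants have just progressed or stopped for another reason, so disease and lenvatinib remain possible causes. In Study 207, Grade 3 or higher TEAEs were 64.5% from any cause and 22.6% treatment-related.
- *That haematologic rates are inflated most.* The last scheduled post-treatment blood counts fall at the Safety Follow-up Visit, which precedes the new therapy. Later counts would come from local care or unscheduled testing, and the documents do not say what the next regimens are.

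**Conclusion.** The point holds as a gap in the analysis definition. Section 9.6.2 counts as treatment-emergent any reported AE or SAE up to 30 days after the last lenvatinib dose, with nothing to distinguish onset before from onset after a new anticancer therapy, in a pooled single-arm summary.

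Its size cannot be determined from the documents. The illustrative 0.4 to 11 point net rise in any Grade 3 or higher incidence rests on assumed switching and event rates, on a base rate borrowed from a different tumor type, and on independence. It also takes the post-switch events as fully reported. Capture is likely to be incomplete once the safety visit has been brought forward, so the realised effect could be smaller, and it would be uneven between participants.

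This is a worthwhile, inexpensive improvement to a descriptive secondary analysis. It gives no ground for doubting the study's efficacy conclusions or for treating its safety data as unusable.

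**What to change.** Leave AE and SAE collection and reporting in Section 8.4.1 as they are. In Section 9.6.2:

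1. Flag each AE whose onset is on or after the start of a new anticancer therapy, taking the date from the off-study therapy record in the Schedule of Activities. State how partial or missing start dates are handled.
2. Tabulate TEAEs and SAEs twice: over the full 30 days after the last dose, and cut at the earlier of 30 days and the start of the new therapy. State in advance which table is the main one.
3. Note beside the full-window table that the scheduled safety visit may have preceded the new therapy, so later events come mainly through the reporting duty in 8.4.1.

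The cost is a short change of wording and one extra set of tables, with no new data collection. The downside is that a delayed lenvatinib effect first seen after the switch appears only in the full-window table, so both tables need to be reported.
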